Table 21 describes the expected coefficients of variation (CV) and mean ratios (MR) between THS 2.2 Menthol and the mCC control arm in COHb, 3-HPMA, MHBMA and S-PMA based on data from a single-center, open-label, randomized, controlled, 2-arm parallel group study to evaluate the exposure to selected smoke constituents in smoking, apparently healthy subjects switching from conventional cigarettes to THS 2.1 compared to subjects continuing to smoke CC for 5 days, the ZRHX-EX-01 study (ClinicalTrials.gov: ID: NCT01780714) sponsored by PMI. The mean ratios and coefficients of variations for THS 2.1/CC are expected to be the same as THS 2.2 Menthol/mCC.

Table 21. Expected Mean Ratios and coefficients of Variation for THS 2.2 Menthol/mCC

THS 2.2 Menthol /mCC	
	MR (CV)
COHb	0.44 (0.14)
3-HPMA	0.28 (0.20)
MHBMA	0.11 (0.47)
S-PMA	0.07 (0.50)

Abbreviations: 3-HPMA = 3-hydroxypropylmercapturic acid; mCC = menthol conventional cigarettes; COHb = carboxyhemoglobin; CV = coefficient of variation; MHBMA = monohydroxybutenyl mercapturic acid; MR = mean ratio; S-PMA = S-phenylmercapturic acid; THS 2.2 = Tobacco Heating System 2.2.

Based on these two sets of assumptions on the mean ratios and coefficients of variations for the four primary BoExp on Day 5, the power to demonstrate a reduction was computed.

The comparison will be run on the per protocol population as defined in Section 12.4.2.

Subjects are expected not to have any reason for exclusion from the per protocol population in the confinement period for THS 2.2 Menthol arm and in ambulatory and confinement condition for the mCC arm.

50% of the subjects are expected to be excluded from the per protocol population in the THS 2.2 Menthol arm in the ambulatory (mostly due to lack of compliance to the randomized product). Thus the expected populations on which the reductions will be assessed as described in Table 22.

Table 22. Sample Size to Assess the Reductions

Sample size to assess the reduction (THS 2.2 Menthol:/mCC)	
COHb	80:40
3-HPMA	80:40
MHBMA	80:40
S-PMA	80:40
Total NNAL	40:40

Abbreviations: 3-HPMA = 3-hydroxypropylmercapturic acid; Total NNAL = total 4-(methylnitrosamino)-1-(3-pyridyl)-1-butanol mCC = menthol conventional cigarettes; COHb = carboxyhemoglobin; MHBMA = monohydroxybutenyl mercapturic acid; S-PMA = S-phenylmercapturic acid; THS 2.2 = Tobacco Heating System 2.2.

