Data and information contained in this document are considered to constitute trade secrets and confidential commercial information, and the legal protections provided to such trade secrets and confidential information are hereby claimed under the provisions of United States law. No part of this document may be publicly disclosed without the written consent of Philip Morris International.

Table 23 describes the expected power to demonstrate a reduction on 5 primary BoExp in smokers switching from CC to THS 2.2 Menthol as compared to those continuing to smoke mCC, using one-sided test with 2.5% type I error probability using the assumptions from YVD-CS01-EU and ZRHX-EX-01 given a sample size of 160 smokers (~80 in THS 2.2, ~40 in CC, and ~40 in the SA arm). Therefore subjects will be enrolled into the study until there are 160 smokers in the FAS population.

Table 23. Expected power (YVD-CS01-EU and ZRHX-EX-01 studies assumptions)

Assumptions	Reduction					
	50%	51%	52%	53%	54%	55%
YVD-CS01-EU	94%	88%	81%	70%	56%	38%
ZRHX-EX-01	98%	97%	92%	76%	41%	6%

Power considerations related to secondary endpoints of biological changes:

The sample size is sufficient to obtain 95% CIs for the ratio between (geometrical) mean levels of primary BoExp in THS 2.2 Menthol and SA with upper and lower limits deviating not more than 18% from the point estimates, with an 80% overall probability of achieving the desired precision of estimating the true mean.

This study has 80% power using a one-sided test with 2.5% type I error probability:

- To detect a 0.631 [mL/min/kg] (29%) difference between THS 2.2 Menthol and mCC in CYP1A2 activity, as measured by the caffeine clearance, assuming a SD of 0.564. Effect size and variability are derived from data obtained in the YVD-CS01-EU study sponsored by PMI.
- To detect a 24.71 [ng/g creatinine] (20%) difference between THS 2.2 Menthol and mCC in 11-DTX-B2, assuming a SD of 43.78, as reported by Saareks et al., 2001. The anticipated effect size of THS 2.2 Menthol is assumed to be about 90% of the effect of smoking cessation reported in the paper by Saareks et al., 2001.

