The PP Set will be the primary analysis for BoExp, and risk markers. The full analysis set (FAS) will be the primary analysis set for compliance to randomization arm. Exposure and questionnaires. Exposure and questionnaires will be described by randomization arm and according to product use categories (see **Table 25**).

A sensitivity analysis will be run on the compliant population for the for BoExp and risk markers.

Safety will be analyzed using the safety population by randomization arm and according to product use categories (see **Table 25**).

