### 12.6.2.5 Risk Markers

The risk markers are:

- Systolic and diastolic blood pressure on Day 0, Day 6, Day 30 Visit, Day 60 Visit, and Day 90 Visit.
- hs-CRP, homocysteine, blood glucose, LDL, HDL, TG, and TC in serum on Day 0, Day 30 Visit, Day 60 Visit, and Day 90 Visit.
- Fibrinogen in plasma on Day 0, Day 30 Visit, Day 60 Visit, and Day 90 Visit.
- HbA1c in blood on Day 0 and Day 90 Visit.
- sICAM-1 in serum on Day 0, Day 6, Day 30 Visit, Day 60 Visit, and Day 90 Visit.
- WBC and platelet count in blood on Day 0, Day 6, Day 30 Visit, Day 60 Visit, and Day 90 Visit.
- 8-epi-PGF2 $\alpha$  and 11-DTX-B2 in 24 hour urine on Day 0, Day 5, Day 30 Visit, Day 60 Visit, and Day 90 Visit (expressed as concentration adjusted for creatinine).

- Body weight and waist circumference on Day -2 and Day 90 Visit.

The results along with the changes from baseline will be listed and summarized. In addition line graphs will be produced for product means (and 95% CI) over all timepoints.

The analysis will compare the results on Day 90 between the THS 2.2 Menthol and mCC arms, and between the THS 2.2 Menthol and SA arms for the FAS and PP set. An ANCOVA model will be used with terms for Baseline, sex, average daily mCC consumption over the last 4 weeks as reported during screening and randomization arm. No adjustment will be made for multiple comparisons.

Blood pressure, HbA1c, LDL, HDL, TG, TC, WBC, body weight and waist circumference will be analyzed in the regular scale. 8-epi-PGF2 $\alpha$ , 11-DTX-B2, sICAM will be analyzed in the logarithmic scale. Other risk markers will be logarithmically transformed prior to analysis if there is evidence of non-normality by means of Shapiro-Wilks test.

The SAS code will be the same as described in Section 12.6.1.1 “**Analysis of Biomarkers of Exposure for Primary Endpoints**”.

LS means for each product along with the difference (THS 2.2 Menthol - mCC) or ratio (THS 2.2 Menthol : mCC) and 95% CI will be presented in the tables along with a forest plot of the results.

If there are any 11-DTX-B2 assessments performed within 5 half-lives since the use of a concomitant medication affecting the production of 11-DTX-B2, the analysis will be repeated by excluding these assessments for both the PP Set and FAS

All tables, figures and analyses will be produced for the FAS and PP Set. Figures will be produced for the PP Set.

The data will be presented in the below outputs:

TFL number	Title
FIGURES	

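### The 80% power stated for 11-DTX-B2 fits 80:40; at the 40:40 the plan expects in the Day 90 per-protocol set it is about 70%, and the 18% THS:SA precision is supported only for the four Day 5 markers

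*Protocol*

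**What the plan says.** Protocol 12.2 gives two planning statements for secondary aims.

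- **Power.** "This study has 80% power using a one-sided test with 2.5% type I error probability", and one of the two items listed under it is "To detect a 24.71 [ng/g creatinine] (20%) difference between THS 2.2 Menthol and mCC in 11-DTX-B2, assuming a SD of 43.78". No day or analysis set is named. The arm sizes in the same section are "given a sample size of 160 smokers (~80 in THS 2.2, ~40 in CC, and ~40 in the SA arm").
- **Precision.** The sample size is said to give 95% confidence intervals for the THS:SA ratio of the primary biomarkers of exposure "with upper and lower limits deviating not more than 18% from the point estimates, with an 80% overall probability".

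The same section also says how many subjects will remain for analysis. It expects that "50% of the subjects are expected to be excluded from the per protocol population in the THS 2.2 Menthol arm in the ambulatory" period, mostly through product non-compliance, and no exclusions "in ambulatory and confinement condition for the mCC arm". Table 22 therefore uses 80:40 for the Day 5 markers and 40:40 for Total NNAL at Day 90. SAP section 8 softens the ambulatory THS loss to at most 50%, keeps 40:40 for Total NNAL, and repeats neither of the two secondary statements.

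On the analysis, SAP section 10 states: "The PP Set will be the primary analysis for BoExp, and risk markers"; Protocol 12.4 agrees. SAP 12.6.2.5 lists 11-DTX-B2 among the risk markers and specifies one inferential time point: "The analysis will compare the results on Day 90 between the THS 2.2 Menthol and mCC arms". That comparison is run on both the FAS and the PP Set by ANCOVA with baseline, sex and cigarette consumption as covariates, and 11-DTX-B2 is analysed on the log scale.

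**The concern.** The 50% ambulatory exclusion is applied to the one Day 90 primary endpoint but not to the power figure for 11-DTX-B2, which under the SAP is also tested at Day 90 with the PP Set as primary. The reason given for the exclusion, lack of compliance with the assigned product, is not specific to Total NNAL.

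A non-significant per-protocol result for 11-DTX-B2 would then be read against a 20% type II risk when the plan's own inputs put it near 30%.

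The 18% precision statement has a separate gap. It refers to the primary biomarkers without restriction, and these include Total NNAL at Day 90, for which no THS/SA variability or SA retention is assumed anywhere.

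**Working it through.** **11-DTX-B2: inputs.** Difference 24.71 and SD 43.78, so d = 24.71/43.78 = 0.564; one-sided alpha 2.5% (Protocol 12.2). Numbers: 80:40 as enrolled; 40:40 in the ambulatory PP population.

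**Formula.** Two-sample t-test with noncentrality d·√(n1·n2/(n1+n2)) on n1+n2−2 degrees of freedom.

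| THS:mCC | Noncentrality | Power |
|---|---|---|
| 80:40 | 2.91 | 82.4% |
| 68:40 | 2.83 | 80.1% |
| 60:40 | 2.77 | 78.2% |
| 40:40 | 2.52 | 70.3% |

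The plan's figure reproduces at 80:40 if 80% is read as a floor. A normal approximation gives 83.0% at 80:40 and 71.4% at 40:40.

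**Detectable difference at 80% power.** 23.9 ng/g at 80:40 and 27.8 at 40:40. If 24.71 is 20% of the mCC mean, that mean is 24.71/0.20 = 123.55, and 27.8/123.55 = 22.5%.

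**Log scale, 40:40.** Using log SD = √ln(1 + CV²) and a true ratio of 0.80, the answer depends on which mean the SD of 43.78 belongs to, which the protocol does not say:

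- mCC mean (123.55): 82%
- average of the two means (111.2): 74%
- THS mean (98.84): 64%

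These figures include no gain from baseline adjustment.

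**FAS, nominally 80:40.** The raw-scale power is 82% only if the full 24.71 difference survives non-compliance. With 75% of the effect left it is 58%; with half, 30%.

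**THS:SA precision at Day 5.** Half-width = exp(t·σ·√(1/n1 + 1/n2)) − 1, with σ = √ln(1 + CV²) and the THS/SA CVs of Table 19 (0.20, 0.33, 0.35, 0.42). S-PMA has the largest CV, 0.42, so σ = 0.403. At 80:40, exp(1.980 × 0.403 × 0.1936) − 1 = 16.7%. From the chi-square distribution of the sample variance, the probability of staying within 18% is 87%; the other three markers are practically certain to do so. The limit met with 80% overall probability, treating the markers as independent, is 17.7%. The 18% statement reproduces.

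**Total NNAL at Day 90.** Table 20 gives a CV of 0.60, but for THS/mCC. No THS/SA value is given, so a range has to be assumed. In Table 19 the THS/SA CVs are 0.50 to 0.66 times the THS/mCC CVs (0.35/0.70 to 0.33/0.50); applied to 0.60 this gives about 0.30 to 0.40.

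| Assumed THS/SA CV | Half-width at 80:40 | Half-width at 40:40 |
|---|---|---|
| 0.30 | 11.9% | 14.0% |
| 0.40 | 15.9% | 18.7% |
| 0.60 | 23.7% | 28.0% |

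The 40:40 column also assumes that all 40 SA subjects stay in the PP Set, which the documents do not state.

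**The case against.** The strongest reply is that nothing is miscalculated: both figures reproduce at 80:40, and the protocol does not tie the 11-DTX-B2 statement to Day 90. The marker is also measured on Day 5, Protocol 4.2 supports it with changes seen within a week, and Protocol 12.6.4 fixes a test sequence only for secondary biomarkers of exposure. The Day 90 restriction comes from the SAP. This stands, and it makes the point one of an unspecified day and population, not of wrong arithmetic. It does not rescue the figure, because the SAP plans no Day 5 inference for risk markers.

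Four stronger readings are tempting and go too far:

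- *11-DTX-B2 is tested only on the PP Set.* The FAS is tested as well; the PP Set is primary.
- *80% power needs the full 80:40.* About 68:40 is enough, and the SAP's wording makes 40 THS a lower bound.
- *The planned test has 70% power.* The 70% belongs to an unadjusted raw-scale comparison. The planned ANCOVA is on the log scale and adjusts for baseline. On the raw scale, a baseline-to-Day-90 correlation of 0.46 would restore 80% at 40:40, but no correlation is given.
- *The 18% precision fails generally, or Total NNAL is shown to miss it.* It holds at Day 5. For Total NNAL the outcome depends on an unstated CV, and the lower part of the plausible range meets 18%.

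It is also fair to say that the consequence is limited: the sample size and the success rule rest on the five primary biomarkers against mCC.

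**Conclusion.** The point holds in a limited form. On the protocol's own raw-scale inputs, the 11-DTX-B2 comparison has 82% power at 80:40 and about 70% at the 40:40 expected in the Day 90 PP Set, so the stated 80% does not describe the primary analysis that the SAP specifies. At 40:40 the difference detectable with 80% power is about 27.8 ng/g (22.5%). This rests on the planned 50% exclusion in the THS arm, none in the mCC arm, and no covariate adjustment; log-scale power at 40:40 lies between 64% and 82% before adjustment.

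The 18% THS:SA statement is sound for the four Day 5 primary biomarkers. For Total NNAL at Day 90 it is unsupported rather than shown to be false: half-widths at 40:40 run from 14% to 28% for assumed CVs of 0.30 to 0.60.

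**What to change.** In Protocol 12.2, or in SAP section 8 if the protocol is closed:

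1. Restate the 11-DTX-B2 power as about 70% for the Day 90 PP Set at 40:40, unadjusted and on raw-scale inputs, or give the detectable difference of 27.8 ng/g. Add that 82% applies only at 80:40 with an undiluted effect. Do not present 82% as the FAS power, since non-compliers would dilute the effect.
2. Limit the 18% THS:SA statement to the four primary biomarkers at Day 5. If a half-width is wanted for Total NNAL at Day 90, give it with the assumed CV and SA number, as a range (for example 14% to 28% at 40:40 for CVs of 0.30 to 0.60).

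The cost is wording. The stated figures become less favourable; the sample size, procedures and primary success rule do not change.

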12.3 Product use

The FDA Draft Guidance on Modified Risk Tobacco Product Applications Draft (Section VI-A-2) (FDA, 2012a), requires that an M RTP Application should contain scientific evidence about the effect the product may have on tobacco use behavior among current tobacco users including consideration of areas such as the expected rates of use of the tobacco product by current tobacco users and the use of the tobacco product in conjunction with other tobacco products.

[figure not shown]
Data and information contained in this document are considered to constitute trade secrets and confidential commercial information, and the legal protections provided to such trade secrets and confidential information are hereby claimed under the provisions of United States law. No part of this document may be publicly disclosed without the written consent of Philip Morris International.

Although subjects are being requested to use solely the product allocated to their respective study arm, it is considered that during the ambulatory period not all subjects randomized to the THS 2.2 Menthol arm might be exclusively using THS 2.2 Menthol at all times during the study. Subjects may concomitantly use THS 2.2 Menthol and CC (dual-use). To assess dual use of THS 2.2 Menthol and CC, PMI has defined dual-use with regards to using THS 2.2 Menthol in the following way:

Dual-use will be calculated as percentage based on their reported THS 2.2 Menthol Tobacco Sticks consumption and the number of conventional cigarettes smoked (menthol and non-menthol) by study period:

- On Day 30 Visit, using the reported number of CC (menthol and non-menthol) and/or Menthol Tobacco Sticks consumption since time of Discharge of Day 6,
- On Day 60 Visit, using the reported number of CC (menthol and non-menthol) and/or Menthol Tobacco Sticks consumption after Day 30 Visit and
- On Day 90 Visit, using the reported number of CC (menthol and non-menthol) and/or Menthol Tobacco Sticks consumption after Day 60 Visit.

Figure 2 presents a detailed overview on the definition of the product use categories.

Figure 2. Product Use Pattern Categorization

The more granular categorization scheme will be used for the definition of the per-protocol population and for the description of the product use patterns observed in the study whereas the less granular scheme will be used for the presentation of other study endpoints (e.g. safety endpoints) to better understand the impact of product.

As the calculation of the sample size was based on the primary objective (reduction of Biomarkers levels in THS 2.2 Menthol relative to mCC), we assumed 50% of the subjects in the THS 2.2 Menthol arm would be using THS 2.2 Menthol exclusively and therefore will be included in the per-protocol population on Day 90.

In order to further optimize the assessment of BoExp and increase the comparability of the levels of biomarkers between THS 2.2 Menthol and SA the confounding effects of the use of any other tobacco or nicotine containing product (other than the assigned product) need to be controlled for. Therefore a subject will be considered abstinent based on the following categorization:

- “Abstinence”: 100% abstinence from tobacco or nicotine containing product use other than the assigned product

- Predominantly abstinent: not more than 0.5 uses of any tobacco or nicotine containing product (other than the assigned product) per day on average and no more than two uses on a single day occur.
- “Not abstinent”: more than 0.5 uses of any tobacco or nicotine containing product (other than the assigned product) per day on average or more than two uses on a single day occur.

The purpose of the defined threshold was to reduce the confounding effects of the use of any other tobacco or nicotine containing product (other than the assigned product). The results of a study PMI conducted in 2011 (PIPA_CEMA_01 study) to evaluate the capacity of the urinary biomarker CEMA to detect smoking of small amounts of CC use (down to 2 CCs) per day was used to help us identify this threshold. The results of this study show that CEMA used as a urinary biomarker of exposure to acrylonitrile is able to discriminate between non-smokers and smokers who have smoked only 2 CCs and 4 CCs with a maximum level of sensitivity and specificity at an optimal threshold of the 2.56 µg/L (CEMA Cmax in non-smokers) for CEMA and 3.76 µg/g for CEMA concentration adjusted for creatinine. For non-smokers CEMA and CEMA concentration adjusted for creatinine were greater than the LLOQ on only one occasion.

12.4 Analysis Population

The per-protocol (PP) population will be the primary analysis for BoExp, and risk markers. The FAS will be the primary analysis set for compliance to randomization arm, exposure and questionnaires. Exposure and questionnaires will be described by randomization arm and according to the product use (exclusive THS 2.2 Menthol, dual-use of THS 2.2 Menthol and mCC, mCC exclusive, SA) groups.

A sensitivity analysis will be run on the compliant population for the for BoExp and risk markers.

The primary population for the assessment of safety will be the safety population. Safety will be summarized presented by randomization arm and according to product use (exclusive THS 2.2 Menthol, dual-use of THS 2.2 Menthol, Menthol and mCC, mCC exclusive, SA).

12.4.1 Full Analysis Set

The FAS consists of all the randomized subjects who had at least one post-randomization product use experience, if randomized to THS 2.2 Menthol or mCC, have at least one valid non-safety assessment (THS 2.2 Menthol, mCC, SA arms)..

12.4.2 Per Protocol Population

The PP population is a subset of FAS and includes all randomized subjects who

- Have had compliance to their randomized arm (see Section 12.1.2 for the definition of non-compliance to randomized arm).
- Have not been misrandomized, and
- Have no major protocol deviation (to be further described in the SAP).

12.4.3 Safety Population

The safety population consists of all the subjects who had at least one exposure to THS 2.2 Menthol (product test at Admission Day). Subjects in the safety population will be analyzed according to actual exposure.

12.4.4 Compliant Population

The compliant population will be a subset of the Per Protocol Population for subjects from the THS 2.2 Menthol arm who are exclusive THS 2.2 Menthol users or exclusive mCC users, as defined in Section 12.3 or for subjects from the mCC arm.

12.5 Primary Analysis

12.5.1 Primary Endpoint Analysis Variables

The primary endpoints are:

- COHb on Day 5
- MHBMA on Day 5
- 3-HPMA on Day 5
- S-PMA on Day 5
- Total NNAL on Day 90.

See Section 3.4.1.

Evaluation criterion:

The study will be considered successful, if the study demonstrates a 50% reduction or more for all five primary BoExp in the THS 2.2 Menthol arm compared to the mCC arm, using a one-sided test with 2.5% type I error probability.

Data and information contained in this document are considered to constitute trade secrets and confidential commercial information, and the legal protections provided to such trade secrets and confidential information are hereby claimed under the provisions of United States law. No part of this document may be publicly disclosed without the written consent of Philip Morris International.

12.5.2 Baseline Comparability

Not applicable.

12.5.3 Descriptive Analysis

Primary endpoints will be summarized as described in Section 12.1.3 on the FAS.

12.5.4 Confirmatory Analysis

The hypothesis to be tested is that the geometric mean level of the BoExp for THS 2.2 Menthol is lower relative to mCC.

For primary BoExp, the hypothesis will be tested on Day 5 for monohydroxylbutenyl-mercapturic acid (MHBMA), 3-hydroxypropylmercapturic acid (3-HPMA), S-phenylmercapturic acid (S-PMA), and carboxyhemoglobin (COHb), and on Day 90 Visit for Total NNAL.

The transformed BoExp data on a natural log scale will be analyzed by means of a generalized linear model using product arm as covariate adjusting for the following baseline information: sex, average cigarette consumption over the previous 4 weeks, and baseline value of endpoint. The test will be declared significant if the contrast THS 2.2 Menthol vs mCC is significant. Estimates of differences between groups will be back-transformed to provide relative effects.

Assumptions of the analysis of variance model will be tested. Markedly non-lognormally distributed BoExp data will be transformed or analyzed by appropriate non-parametric methods.

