6.3 Method for Assigning Subjects to Study Arms

When all the eligibility criteria have been met, randomization will be done through the Interactive Web and Voice Response System (IWRS) on Day 0 at any time during the day. Subjects will be informed of their randomized study arm in the morning of Day 1, prior to 06:30 AM.

Subjects will be randomized to one of the 3 study arms THS 2.2 Menthol:mCC:SA in a 2:1:1 ratio. Stratified randomization will be conducted by sex and by daily average cigarette consumption in the 4 weeks prior to the Screening Visit (those smoking 10 to 19 mCC and those smoking >19 mCC per day) reported by the subject. In each arm, each sex and each of the smoking strata should have a quota applied to ensure they represent at least 40% of the study population.

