12.1.5 Significance Level for Inferential Analysis

Unless stated otherwise, all statistical tests will be two-sided and conducted at the 5% level, and all quoted confidence intervals will be two-sided 95% confidence intervals.

The primary endpoints will be tested using a multiple testing procedure to preserve the overall alpha level by simultaneously testing the endpoints using a closed procedure with each test performed at an one-sided alpha level of 2.5%. This implies that statistical significance is required for all primary endpoints in order to be able to make confirmatory claims about any of the endpoints.

Further details will be provided in the SAP.

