12.2 Determination of Sample Size and Power Consideration

The following discussion addresses the ability to demonstrate on Day 5 a reduction of at least 50% on four selected primary BoExp and on Day 90 on a fifth primary BoExp in smokers switching from mCC to THS 2.2 Menthol as compared to smokers continuing to smoke mCC.

Table 19 describes the expected coefficients of variation (CV) and mean ratios (MR) between THS 2.2 Menthol and the two control arms in COHb, 3-HPMA, MHBMA, and SPMA on Day 5 based on data from a controlled, randomized, open-label, 3-arm parallel single-center confinement study to investigate exposure to selected smoke constituents in smokers switching from CCs to smoking article (SMAR) cigarettes for 5 days, the YVD-CS01-EU study (ClinicalTrials.gov: ID: NCT00812279) sponsored by PMI. The mean ratios and coefficients of variations for SMAR/CC are expected to be the same as THS 2.2 Menthol/mCC.

Table 19. Expected Mean Ratios and Coefficients of Variation for THS 2.2 Menthol/mCC

	THS 2.2 Menthol /mCC	THS 2.2 Menthol/SA
	Mean Ratio (CV)	Mean Ratio (CV)
COHb	0.40 (0.32)	2.10 (0.20)
3-HPMA	0.30 (0.50)	1.70 (0.33)
MHBMA	0.15 (0.70)	1.00 (0.35)
S-PMA	0.20 (0.70)	1.15 (0.42)

Abbreviations: 3-HPMA = 3-hydroxypropylmercapturic acid; mCC = menthol conventional cigarettes; COHb = carboxyhemoglobin; CV = coefficients of variation; MHBMA = monohydroxybutenyl mercapturic acid; MR = mean ratios; S-PMA = S-phenylmercapturic acid; SA = smoking abstinence; THS 2.2 = Tobacco Heating System 2.2.

Table 20 describes the expected coefficients of variation (CV) and mean ratios (MR) between THS 2.2 Menthol and the mCC control arm in Total NNAL on Day 90 based on data from a Philip Morris USA-sponsored randomized, controlled, switching, open-label, parallel-group, single-center study in 90 male and female adult smokers evaluated six biomarkers of tobacco smoke exposure over a 12-week period (Frost-Pineda et al., 2008). The mean ratios and coefficients of variations for EHCJLI /CC are expected to be the same as THS 2.2 Menthol/mCC.

Table 20. Expected Mean Ratios and Coefficients of Variation for THS 2.2 Menthol/mCC

THS 2.2 Menthol /mCC	
	MR (CV)
Total NNAL	0.30 (0.60)

Abbreviations: Total NNAL = total 4-(methylnitrosamino)-1-(3-pyridyl)-1-butanol; MR = mean ratio; THS 2.2 = Tobacco Heating System 2.2; mCC = menthol conventional cigarettes; CV = coefficient of variation.

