### 12.6.1 Primary Analyses

#### 12.6.1.1 Analysis of Biomarkers of Exposure for Primary Endpoints

The BoExp (COHb in blood and urinary concentrations of MHBMA, 3-HPMA, S-PMA and Total NNAL) used for the primary analysis will be summarized as detailed in Section 12.1.3 “Descriptive Statistics”. The listing of the COHb data will have a flag for whether a subject’s COHb was <2%.

The baseline is as defined in Section 12.1.4 “Definitions for Statistical Data Analysis”.

The primary endpoints will be log-transformed (basee) prior to analysis. The analysis will compare the evening COHb level (20:00-21:30 PM) on Day 5; and urinary concentrations of MHBMA, 3-HPMA and S-PMA adjusted for creatinine on Day 5 and urinary concentrations of Total NNAL adjusted for creatinine on Day 90 Visit between the THS 2.2 Menthol and mCC arms for the PP Set. An analysis of covariance (ANCOVA) (Snedecor and Cochran 1982) model will be used with terms for the log-transformed baseline value, sex, average daily mCC consumption over the last 4 weeks as reported during screening and randomization arm.

The SAS code to be used for the THS 2.2 Menthol and mCC data is shown below:

```
Proc glm data=_data_;
Class randomization_arm sex cigarette_cons;
Model log_biomarker = log_baseline sex cigarette_cons
randomization_arm;
Lsmean randomization_arm / pdiff =control('mCC') alpha=0.05 cl;
Run;
```

The least squares (LS) means and estimate of the difference and the 95% CI will be back-transformed. The geometric LS means for each randomization arm along with the ratio

(THS 2.2 Menthol : mCC), two-sided 95% CI and one-sided p-value will be presented in the tables. THS 2.2 menthol : mCC effects will be graphed in a forest plot.

All figures, summaries and analyses will be performed on the PP Set. Additional descriptive statistics will be provided within the secondary analysis.

The data will be presented in the below outputs:

TFL number	Title
FIGURES	
15.1.1.1	Forest Plot of Statistical Analysis of Biomarkers of Exposure on Day 5 and Day 90 – PP Set
15.1.1.2	Biomarkers of Exposure Geometric Mean and 95% CI – PP Set
TABLES	
15.2.3.1.1	Analysis of COHb, MHBMA, 3-HPMA, S-PMA and Total NNAL on Day 5/90 Visit for THS 2.2 Menthol versus mCC for the Primary Objective – PP Set
15.2.4.1.1	Descriptive Statistics of Blood COHb (%) – PP Set
15.2.4.1.1.1	Descriptive Statistics of Blood COHb (%) by Sex – PP Set

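### The four Day 5 primary tests assume equal variance at a planned 80:40; if mCC is the more variable arm, as Table 19 suggests on one reading, one-sided error is about 3–6% rather than 2.5%

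*Protocol*

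**What the plan says.** Protocol 12.5.4 sets the confirmatory model: "The transformed BoExp data on a natural log scale will be analyzed by means of a generalized linear model using product arm as covariate", adjusted for sex, cigarette consumption and the baseline value. SAP 12.6.1.1 gives the code for the THS and mCC data as PROC GLM, with a statement that begins "Model log_biomarker = log_baseline sex cigarette_cons" and continues with the arm term. This has a single residual variance. The PROC MIXED sensitivity analysis in SAP 12.6.1.3 repeats the same model terms and also has no arm-specific variance.

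Protocol 12.5.4 promises to test the model assumptions, but the only remedy it names (transformation or a non-parametric method) is for data that are markedly not lognormal. The SAP's primary analysis section has no variance check or fallback.

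The trial succeeds if it "demonstrates a 50% reduction or more for all five primary BoExp", "using a one-sided test with 2.5% type I error probability". Protocol 12.1.5 adds: "This implies that statistical significance is required for all primary endpoints in order to be able to make confirmatory claims about any of the endpoints".

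On allocation: "Subjects will be randomized to one of the 3 study arms THS 2.2 Menthol:mCC:SA in a 2:1:1 ratio". Table 22 of the protocol therefore has 80:40 for COHb, 3-HPMA, MHBMA and S-PMA. Total NNAL is at 40:40 because "50% of the subjects are expected to be excluded from the per protocol population in the THS 2.2 Menthol arm in the ambulatory" period. On variability: "Table 19 describes the expected coefficients of variation (CV) and mean ratios (MR) between THS 2.2 Menthol and the two control arms". There is one CV per comparison and none per arm.

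**The concern.** A pooled variance is weighted towards the larger arm, while the variance of the contrast depends most on the smaller arm. If the 40 mCC subjects vary more than the 80 THS subjects, the pooled standard error is too small. The test then exceeds its nominal error and the confidence intervals are too narrow. This is so whatever ratio is tested, because the same standard error is used.

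Table 19 gives reason to expect this pattern. All of its Day 5 CVs come from one three-arm study, THS is in both comparisons, and the THS/mCC CV exceeds the THS/SA CV on all four endpoints.

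The requirement that all five endpoints succeed does not remove the problem. If COHb sat exactly at the 0.50 boundary and the other four were clearly reduced, study-level error would be close to the COHb error. COHb is planned nearest the margin, with an assumed ratio of 0.40 in Table 19 and 0.44 in Table 21.

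**Working it through.** **1. Reproducing the plan's power.** Use a log-scale SD of √ln(1+CV²), common to both arms, a distance of ln(0.5/MR), one-sided 2.5%, and the Table 22 sample sizes.
- COHb (Table 19): SD √ln(1+0.32²) = 0.312; SE 0.312 × √(1/80+1/40) = 0.0605; ln(0.5/0.40) = 0.223; power 95.8%.
- Total NNAL: power 98.5%. The other three are about 100%.
- Joint power: 0.958 × 0.985 = 94.3%, against 94% in Table 23. The Table 21 set gives 98.2%, against 98%.

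The planned power therefore reproduces with one common SD for both arms.

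**2. Splitting the Table 19 CVs by arm.** Assumption: each CV is pooled within the two arms of its comparison, with equal weights. Let A = ln(1+CV²) for THS/mCC and B = ln(1+CV²) for THS/SA. Then vT + vC = 2A and vT + vS = 2B, where T, C and S are THS, mCC and SA.
- Since vS cannot be negative, vT ≤ 2B and R = vC/vT ≥ A/B − 1.
- If THS and SA vary alike, vT = B and R = 2A/B − 1.

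**3. Actual error of the pooled test.** Let q = pooled SE / true SE, where the true SE is √(vT/80 + vC/40). The one-sided error is P(Z > 1.96q).

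COHb with vT = vS: vT = 0.0392 and vC = 2 × 0.0975 − 0.0392 = 0.1558. The pooled variance is (79 × 0.0392 + 39 × 0.1558)/118 = 0.0777, so the pooled SE is √(0.0777 × 0.0375) = 0.0540. The true SE is 0.0662, so q = 0.815 and the error is P(Z > 1.598) = 5.5%. Coverage of the 95% interval is 1 − 2 × 0.055 = 89%.

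| Endpoint | CV THS/mCC | CV THS/SA | A | B | R, lower bound | Error | R, THS = SA | Error |
|---|---|---|---|---|---|---|---|---|
| COHb | 0.32 | 0.20 | 0.0975 | 0.0392 | 1.49 | 3.3% | 3.97 | 5.5% |
| 3-HPMA | 0.50 | 0.33 | 0.2231 | 0.1034 | 1.16 | 2.8% | 3.32 | 5.1% |
| MHBMA | 0.70 | 0.35 | 0.3988 | 0.1156 | 2.45 | 4.5% | 5.90 | 6.2% |
| S-PMA | 0.70 | 0.42 | 0.3988 | 0.1625 | 1.45 | 3.3% | 3.91 | 5.5% |

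**4. Other readings of the CVs.** With 2:1 weights and vT = vS, the error is 5.7–6.8%. If the two CVs are read directly as the mCC and THS CVs, it is 4.2–5.2%.

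**5. Baseline adjustment.** The variance that matters is the ANCOVA residual. I simulated the ANCOVA under equal weights and vT = vS. The correlations with baseline are my assumptions.
- Correlation 0–0.5, the same in both arms: 5.1–6.5%.
- mCC 0.7–0.9 and THS 0.3–0.5: 3.2–5.5%. COHb is 4.5% at 0.7 and 3.6% at 0.9.
- A heteroscedasticity-robust (HC2) standard error in the same runs: 2.2–2.7%.

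By formula at 80:40, a residual ratio of 1 gives 2.5%, and a ratio of 0.5 gives 1.4%.

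**6. Total NNAL.** At 40:40 the formula gives 2.5% for any variance ratio; simulation gives 2.5–2.7% for ratios of 2 to 6.

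**The case against.** The documents do not establish that mCC is the more variable arm. Protocol 12.2 does not say whether a CV is pooled, taken from one arm or baseline-adjusted. If the CVs describe the reference arms, they say nothing about THS. The lower bound in step 2 also needs equal weights, and the arm sizes of the source study are not given. Equal variance in THS and SA, which gives the upper figures, is not stated anywhere.

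The second planning set, Table 21, has no SA column and cannot be split by arm. Its COHb CV of 0.14 limits the mCC log variance to 2 × ln(1+0.14²) = 0.039 under the same algebra, against 0.156 in step 3. That does not contradict a high ratio, but it shows that the inference rests on one study of a different product.

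Continuing mCC smokers may correlate strongly with their own baseline, which shrinks the residual gap. Combined with the lower-bound ratios, this could bring the residual ratio below 1, and the test would then be conservative.

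All of this stands. A reader might infer that the plan's own CVs prove mCC more variable and that the error doubles. The documents support only the conditional statement.

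A reader might also infer that the stated power is wrong. The plan states only joint five-endpoint power. With unequal-variance standard errors (equal weights, vT = vS) it falls from 94% to about 91%, still above the 80% target.

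The protocol's promise to test assumptions covers equal variance in principle. It names no action if that check fails, so the gap remains.

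**Conclusion.** The point holds as a conditional one. The primary model has one residual variance at a planned 80:40, and no remedy is written for unequal variance. If the Table 19 CVs are two-arm pooled with equal weights, the four Day 5 tests run at about 3–6% instead of 2.5%. COHb is at 3.3% at the lower bound and 5.5% if THS and SA vary alike. The excess is smaller if mCC values correlate strongly with baseline, and there is none if the residual variances are equal.

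The practical consequence is mainly for COHb and for the width of the Day 5 THS:mCC intervals. The assumed ratios for 3-HPMA, MHBMA and S-PMA run from 0.07 to 0.30 over the two planning sets, so inflation there is unlikely to change the success decision. Total NNAL is not affected while it stays near 40:40.

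**What to change.** In SAP 12.6.1.1, and wherever the model is reused for the biomarkers of exposure, pre-specify the same ANCOVA with arm-specific residual variances for the THS versus mCC contrast. Use PROC MIXED with the same MODEL statement, the option `ddfm=satterthwaite`, and the added line `repeated / group=randomization_arm;`. HC3 standard errors are an acceptable alternative. Add a matching sentence to Protocol 12.5.4 and keep PROC GLM as a sensitivity analysis.

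The cost is one line of code, one sentence, a few degrees of freedom, and slightly wider intervals if the variances do differ. The analysis is valid whether or not they differ. Fixing it in advance is easier to defend than choosing a remedy after the data are seen, particularly as SAP section 9 records that the study team was accidentally unblinded.
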